7. STATISTICS AND DATA ANALYSIS

Sample size: This is a novel mechanistic study where the primary endpoint is the effect of celecoxib on endothelial function measured using the EndoPAT device. We anticipate that we will require n=20-40 in each study arm to detect a difference based on previous work using similar drugs and alternative measurement approaches. For example Carlsson and Wennmalm (1983)¹⁹ showed a reduction in endothelial function with ibuprofen (effect size: 0.80 standard deviations) and diclofenac (effect size: 1.06 standard deviations). This equates to a power of 72-92% at n=20 and 95-100% at n=40 to detect a difference between groups at a nominal significance threshold of p<0.05. As we are using a different drug and an alternative measurement platform, power can only be estimated broadly. As such, we will perform an interim analysis of data after studying n=20 volunteers per group during the 'wash out' period. At this point, actual effect size and variance will be determined and experimental power re-calculated. If our primary endpoint is not achieved, we may revise our endpoints and/or if additional power is required, we will reserve the option to recruit up to an additional n=20 volunteers per group. Dependent upon the results the interim analysis may also serve as a stop-go checkpoint for continuation of the L-arginine arm of the study.

Data analysis: Data will be analysed according to approaches applicable to the measurement. This includes standard parametric and non-parametric tools (including Fisher's exact tests, Student's t-tests, 1-way and 2-way ANOVAs, Mann Whitney U-tests and Kruskall-Wallis tests) as well as specialised tests for large omic data sets (including modified t-test with false discovery correction where appropriate). Across all tests differences will be considered significant where p<0.05.

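### Section 7 states no baseline adjustment for the primary EndoPAT comparison, although Visit 1 EndoPAT is collected; ANCOVA costs almost nothing and gains materially if the Visit 1–Visit 2 correlation is about 0.5 or more

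*Combined protocol and SAP*

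**What the plan says.** Section 7 (Sample size) says that "the primary endpoint is the effect of celecoxib on endothelial function measured using the EndoPAT device". It gives power of 72-92% at n=20 and 95-100% at n=40, for effects of 0.80 and 1.06 SD, "to detect a difference between groups at a nominal significance threshold of p<0.05".

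Section 7 (Data analysis) is the only analysis text. The list opens with "This includes standard parametric and non-parametric tools" and goes on to Fisher's exact tests, t-tests, "1-way and 2-way ANOVAs, Mann Whitney U-tests and Kruskall-Wallis tests". No test is assigned to the primary endpoint. The section does not say whether the outcome is the Visit 2 value or the change from Visit 1, and no baseline covariate is named.

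The baseline value exists. The study flowchart has EndoPAT at screening and at Visits 1 to 4. Section 3 places measurements at baseline and after the last dose, and Section 4 (Re-enrolment) pairs Visits 1 and 2 seven days apart.

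Section 3 plans twenty volunteers per arm. Section 7 adds that "we will perform an interim analysis of data after studying n=20 volunteers per group", at which point "actual effect size and variance will be determined and experimental power re-calculated". Depending on the result, "we will reserve the option to recruit up to an additional n=20 volunteers per group", and the look "may also serve as a stop-go checkpoint for continuation of the L-arginine arm of the study".

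**The concern.** A baseline value of the primary outcome is collected on every volunteer, and the plan does not say that it will be used. The named tests lead to one of three analyses:

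- **Visit 2 only.** Visit 1 is ignored.
- **Change score.** A t-test on the change. A repeated-measures 2-way ANOVA gives the same test through its arm-by-visit interaction when there are two visits.
- **Ordinary 2-way ANOVA by arm and visit.** The pairing within volunteers is ignored, and the interaction test is badly conservative when r > 0.

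None of these is as dependable as ANCOVA when r is unknown. The choice also feeds the interim. The variance that goes into the power re-calculation depends on the analysis, so the same data could point to different recruitment decisions, and the model would be chosen after the data are seen.

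**Working it through.** **Inputs from the documents:** 20 per arm (Section 3; also the interim size in Section 7), up to 40 per arm, effects of 0.80 and 1.06 SD, threshold 0.05 (Section 7). **Assumed:** r, the Visit 1–Visit 2 correlation, at 0, 0.3, 0.5 and 0.7; equal SD at both visits; two-sided tests.

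**1. The plan's own figures.** Normal approximation, power = Φ(d√(n/2) − 1.96):

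- n=20: Φ(2.530 − 1.960) = 71.6%; Φ(3.352 − 1.960) = 91.8%.
- n=40: Φ(3.578 − 1.960) = 94.7%; Φ(4.741 − 1.960) = 99.7%.

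These match 72-92% and 95-100%. The rest of the working uses the noncentral t distribution, which gives slightly lower values (69.3% and 90.4% at n=20).

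**2. The three valid analyses**, with d in between-person SD:

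- Visit 2 only: noncentrality d√(n/2), on 2n−2 df.
- Change score: replace d by d/√(2(1−r)), on 2n−2 df.
- ANCOVA: divide the noncentrality by √[(1−r²)(1 + 1/(2n−4))], on 2n−3 df. The last factor allows for chance imbalance at baseline.

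Example at n=20, d=0.80, r=0.5: ANCOVA noncentrality = 2.530/√(0.75 × 1.0278) = 2.88 on 37 df, giving 80.1%.

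| n per arm, effect | Analysis | r=0 | r=0.3 | r=0.5 | r=0.7 |
|---|---|---|---|---|---|
| 20, 0.80 SD | ANCOVA | 68% | 72% | 80% | 93% |
| | Visit 2 only | 69% | 69% | 69% | 69% |
| | Change score | 41% | 55% | 69% | 89% |
| 20, 1.06 SD | ANCOVA | 90% | 92% | 96% | 99% |
| | Visit 2 only | 90% | 90% | 90% | 90% |
| | Change score | 64% | 79% | 90% | 99% |
| 40, 0.80 SD | ANCOVA | 94% | 96% | 98% | >99% |
| | Visit 2 only | 94% | 94% | 94% | 94% |

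ANCOVA breaks even with Visit 2 only at r of about 0.17.

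**3. What the interim re-calculation would see.** Volunteers per arm for 80% power at 0.80 SD, for r = 0/0.3/0.5/0.7: ANCOVA 27/24/20/15; Visit 2 only 26; change score 51/36/26/16. Expected 95% CI half-width at n=20: ANCOVA 0.65/0.62/0.56/0.46 SD; Visit 2 only 0.64; change score 0.90/0.75/0.64/0.49.

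**4. A smaller true effect** (assumed 0.5 SD, r=0.5). From Visit 2 only to ANCOVA: 34% to 42% at n=20, and 60% to 72% at n=40.

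**5. Ordinary 2-way ANOVA.** Its interaction test takes the variance as 4σ²/n, whereas the true variance is 4(1−r)σ²/n. Simulation at n=20 per arm (20,000 runs) gave rejection under no effect of about 5/2/0.7/0.1% for r = 0/0.3/0.5/0.7, and power at 0.80 SD of about 42/41/39/37%. It is not a substitute for the change score.

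**6. Validity.** Under no effect (40,000 runs, r=0 and 0.5), Visit 2 only, change score and ANCOVA each rejected in 4.9–5.1% of runs.

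**7. If the quoted SDs are SDs of change.** At n=20 and 0.80: ANCOVA 93/85/80/75%, Visit 2 only 94/83/69/48%, change score 69%. ANCOVA is again best or within about 1 point of best.

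**The case against.** The strongest reply has three parts.

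First, the list in Section 7 is open, so ANCOVA is permitted, and the plan contradicts nothing. That stands: a reader might infer that ANCOVA is excluded, and the text does not say so. But permitting it is not choosing it, and the tests that are named lead elsewhere.

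Second, the gain depends on an r that the documents do not give, and excluding LnRHI below 0.51 at screening may lower r. That also stands. At r=0.3 and 0.80 SD the gain over Visit 2 only is just 3 points. It does not favour either alternative, though: ANCOVA is best or within about 1 point of best at every r shown, while the others can lose far more.

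Third, this is a preference among valid methods in a mechanistic study that itself says power can be estimated only broadly. This limits the severity but does not remove the point.

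Four stronger readings are tempting and are not supported:

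- *The unadjusted analysis is biased.* Randomisation protects it.
- *The stated power shows that a Visit 2-only analysis was intended.* The match holds for any outcome whose effect is in units of its own SD, and Section 7 does not say which SD it used.
- *Any 2-way ANOVA already amounts to a change-score test.* Only the repeated-measures form does, and Section 7 does not specify it.
- *The gain is mainly an interim matter.* Twenty per arm is also the base design, and with a smaller true effect the gain at 40 per arm can be the larger one.

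**Conclusion.** The point holds as a cheap improvement that should be made before the interim; it is not an error of validity. With 20 per arm and 0.80 SD, ANCOVA on Visit 1 changes power relative to Visit 2 only by about −1, +3, +11 and +23 points at r = 0, 0.3, 0.5 and 0.7. At 1.06 SD the changes are about −1, +2, +6 and +9 points. Against the change score it gains most when r is low: 27 points at r=0 (68% against 41%, 0.80 SD). At 40 per arm and 0.80 SD little is left to gain, but at 0.5 SD and r=0.5 the gain is 12 points.

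The sizes rest on the assumed r, on equal SDs at the two visits, and on effects that Section 7 borrows from other drugs and another measurement approach. That ANCOVA is the safe choice does not depend on knowing r within the range shown.

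**What to change.** Before the interim, state in Section 7:

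1. The primary analysis of the celecoxib effect is ANCOVA of Visit 2 EndoPAT on arm, with Visit 1 EndoPAT as covariate. The result is the adjusted difference with its 95% CI.
2. Which EndoPAT summary is used. LnRHI is the only one the documents name, and only as an exclusion threshold.
3. The interim power re-calculation uses the residual SD of that model.
4. Whether the 0.80 and 1.06 SD effects refer to Visit 2 values or to change.

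The cost is wording only, with no new visits or data. Statistically it is one degree of freedom, and about 1 point of power at 20 per arm if r turns out to be near 0.

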8. REGULATORY ISSUES

Ethics Approval

The Study Coordination Centre has obtained approval from the xxx Research Ethics Committee (REC) and Health Research Authority (HRA). The study must also receive confirmation of capacity and capability from each participating NHS Trust before accepting participants into the study or any research activity is carried out. The study will be conducted in accordance with the recommendations for physicians involved in research on human subjects adopted by the 18th World Medical Assembly, Helsinki 1964 and later revisions.

Consent

Consent to enter the study must be sought from each participant only after a full explanation has been given, an information leaflet offered and time allowed for consideration. Signed participant consent should be obtained. The right of the participant to refuse to participate without giving reasons must be respected. After the participant has entered the study the clinician remains free to give alternative treatment to that specified in the protocol at any stage if he/she feels it is in the participant's best interest, but the reasons for doing so should be recorded. In these cases the participants remain within the study for the purposes of follow-up and data

analysis. All participants are free to withdraw at any time from the protocol treatment without giving reasons and without prejudicing further treatment.

Confidentiality

The Chief Investigator will preserve the confidentiality of participants taking part in the study.

All participant information collected during the study will be kept strictly confidential, and any information about participants which leaves the facility will have their name and address removed. Only authorised persons such as researchers, the sponsor and research and development audit will have access to the data.

Study data will be collected using REDCap which is a mature and secure web application for clinical trial data capture. Data is stored on the secure encrypted imperial college server. All data held in REDCap is anonymised. Only members of the research team will have access to data.

Written study records will be kept in a locked cabinet. Any written study records will be pseudonymised such that data, samples and records of participants will be known by a study number with the key known only to the study team and kept separately from the pseudonymised study data. Participant Identifiable data (e.g consent forms) will also be kept in a locked cabinet with restricted access. After the study data have been analysed and published, all written and electronic study records will be kept for 10 years by Imperial College London.

Pseudonymised electronic records of the data will be kept on a computer at Imperial College London which is protected by a firewall. If the electronic data are used in further research then further REC approval will be sought.

Indemnity

Imperial College London holds negligent harm and non-negligent harm insurance policies which apply to this study.

Sponsor

Imperial College London will act as the main Sponsor for this study.

Funding

The British Heart Foundation is funding this study.

Audits

The study may be subject to inspection and audit by Imperial College London under their remit as sponsor and other regulatory bodies to ensure adherence to GCP.

